11.2 SUBJECT DEMOGRAPHICS/OTHER BASELINE CHARACTERISTICS

Descriptive statistics for background and demographic variables such as age, sex, race, ATHF level and HAM-D₁₇ total score and subscores at baseline will be presented for the ITT and PP populations. The standard descriptive statistics such as mean, standard deviation, median, quartiles, minimum, and maximum will be used to summarize the continuous variables. For discrete variables, the frequency and percentage of subjects in each category will be calculated.

The demographic profile of subject enrolled in the present study will be compared in an exploratory descriptive manner to the non-Naïve cohort of subjects enrolled in the previous NEST study to assess comparability of study populations.

For patients entering the follow-up open-label phase, descriptive statistics for background and demographic variables will be presented according to previous double-blind treatment for the all sTMS-treated subject population.

11.3 TREATMENTS (STUDY PROCEDURES, OTHER CONCOMITANT THERAPIES)

A data listing of the study treatment administered will be provided. The cumulative number and percentage of subjects exposed to study treatment by time interval and descriptive statistics of duration of exposure to study treatment will be provided by treatment group. The number and percentage of subjects receiving concomitant medications and significant non-drug therapy will also be summarized.

For subjects who receive open label sTMS treatment, data on study treatment administered and duration of exposure to study treatment will be summarized for the all sTMS-treated subject population using similar displays as for the double-blind treatment. These data will be categorized into two groups: those who had received sTMS during the double-blind treatment phase and those who received sham during the double-blind treatment phase.

11.4 ANALYSIS PLAN

Definition of Primary Endpoint

The primary endpoint is clinical response, defined by 50% or greater reduction on the HAM-D₁₇ total symptom scores through 6 weeks of treatment.

Statistical Hypotheses

We will test the null hypothesis that the active sTMS treatment group does not differ from the sham group in the proportion of subjects who show 50% or greater improvement from baseline to Week 6 on the HAM-D₁₇ total score. The corresponding alternative hypothesis is that the active sTMS treatment group has a greater proportion of patients than the sham group with respect to the proportion of subjects who show 50% or greater improvement from baseline to Week 6 on the HAM-D₁₇ total score. The hypotheses can be expressed numerically as:

$$H_0: \pi_A - \pi_S = 0$$

and

$$H_a: \pi_A - \pi_S \neq 0$$

where π_A is the proportion of subjects who show 50% or greater improvement in mean HAM-D₁₇ total score from baseline (Day 0) to Week 6 for the active treatment and π_S is the equivalent value for the sham-controlled group.

Sample Size Calculation

The calculation of sample size requirements for this confirmatory study is based on the results observed in the PP analysis of non-Naïve subjects enrolled in the previous NEST trial. In that population, 34% of subjects treated with active sTMS were categorized as responders, whereas only 8% of sham treated subjects responded. Assuming true population response rates of 34% for sTMS and 8% for Sham, power analysis indicates that a PP sample size of 92 subjects (46 subjects per treatment group evaluable at week 6) yields 81% power to demonstrate superiority of sTMS, where the statistical test is Fisher's exact test at a two-sided 0.05 level of significance. A total of 120 subjects will therefore be enrolled in the study to account for potential drop-outs and noncompliance prior to Week 6.

Adaptive Sample Size Re-estimation

Due to uncertainty regarding the expected sham response rate and resulting treatment effect differential, this study will utilize an adaptive design that allows one interim sample size re-estimation after a minimum of 70 subjects have been enrolled and completed 6 weeks of treatment (or dropped out prior to 6 weeks). The pre-specified maximum allowable adjusted sample size following re-estimation will be 240 enrolled, or two times the initial planned sample size of 120 enrolled, based on practical resource constraints and the desire to achieve a minimum differential of 12% between active and sham response rates. The re-estimation of sample size will be conducted by an independent biostatistician following a pre-specified plan as described by Mehta and Pocock, 2010.

Specifically, at the interim stage the conditional power (CP) for obtaining a significant beneficial effect of sTMS over sham with respect to the primary endpoint will be calculated. This conditional power will be calculated using formula (6) in Mehta and Pocock (2010) under the assumption that the interim estimate of the risk difference is the true population risk difference. The study will not be stopped for overwhelming efficacy or futility at this interim stage. Based on Table 1 of Mehta and Pocock (2010), if the $CP \leq 36\%$ or $CP \geq 90\%$, the study will continue to its original planned sample size of 120 enrolled subjects. Otherwise if $36\% < CP < 90\%$ (the Mehta and Pocock "promising zone"), then the sample size may be increased in order to obtain 90% CP, up to a maximum of 240 enrolled subjects. This approach to sample size increase does not inflate the overall Type I error.

The sponsor and investigators will remain blinded to the interim results for the duration of the ongoing study.

11.5 GENERAL STATISTICAL CONSIDERATIONS

The data analysis will be performed after all subjects have completed the Week 6 visit or have withdrawn from study prior to completion of 6 weeks of follow-up. The standard descriptive statistics such as mean,

standard deviation, median, quartiles, minimum, and maximum will be used to summarize the continuous variables. For discrete variables, the frequency and percentage of patients in each category will be calculated.

All statistical tests will be two-sided with a significant level of 0.05 unless otherwise specified. All confidence intervals will be two-sided with a confidence level of 95%, unless otherwise specified.

Primary Efficacy Analysis

The primary efficacy analysis will be a test of the hypotheses:

$$H_0: \pi_A - \pi_S = 0$$

and

$$H_a: \pi_A - \pi_S \neq 0$$

where π_A is the proportion of subjects who show 50% or greater improvement in mean HAM-D₁₇ total score from baseline (Day 0) to Week 6 for the active treatment and π_S is the equivalent value for the sham-controlled group. The test of the null hypothesis will be based on Fisher's exact test at a two-sided 0.05 level of significance. In addition, the observed response rates and two-sided 95% confidence intervals of the risk difference between treatments will be presented, calculated using the Wilson method as discussed in Newcombe (1998).

To assess homogeneity of results across study centers, the number and percentage of primary responders in each study center will be reported by treatment group. An assessment of treatment-by-center interaction will be carried out at the 0.15 level of significance using the Breslow-Day test. Study centers with less than 10 subjects per center will be pooled with other center(s) by geographic region. The pooling will be detailed in the statistical analysis plan and will be carried out before the blind is broken.

This efficacy analysis will be performed on the ITT and PP (primary) analysis sets. For the ITT, the main analysis will exclude missing data. There will be no missing primary endpoint data in the PP population, by definition. Due to the confirmatory intent of this study, the PP analysis set will be used for initial sample size estimation, for sample size re-estimation, and to assess consistency in a descriptive manner with the previous NEST results showing superiority of active over sham response rates for non-naïve subjects receiving treatment as prescribed.

Additional Endpoint Analyses

The following analyses will be carried out for each of the ITT and PP (primary) populations. There will be no imputation for missing data or adjustments for multiple comparisons.

Additional Endpoints to be studied are:

- The change in mean symptom scores on the HAM-D₁₇ through 6 weeks of treatment
- The change in mean symptom scores on the MADRS through 6 weeks of treatment.
- Clinical response, defined by 50% or greater reduction on the MADRS total symptom scores through 6 weeks of treatment.
- Effectiveness of Blinding questionnaire

Descriptive statistics (sample size, mean, median, quartiles, standard deviation, minimum, maximum) of the mean change in HAM-D₁₇ and MADRS from baseline to Week 6 will be presented. Change from baseline in the HAM-D₁₇ and MADRS total scores will be compared across treatment groups using a MMRM model with terms for treatment, investigative center, visit, and the treatment by visit interaction (visits in the open-label phase will be excluded for the primary double-blind analysis). The model will also include baseline HAM-D₁₇ (or MADRS) score as a covariate and subject will be a random effect. An unstructured covariance matrix will be used for the within-subject correlation. Kenward-Rogers'

approximation will be used to estimate degrees of freedom. The LSMEANS statement for the treatment-by-visit interaction will be employed to examine differences across treatments at specific time points, with the focus being on the Week 6 change from baseline. Parameter estimates will be presented and two-sided 95% confidence intervals will be constructed using model estimates for the mean and residual error. Tests of hypotheses will be two-sided and will be based on the contrasts between active sTMS and sham within the model.

For MADRS response rate through 6 weeks of treatment, the number and percentage of responders will be calculated and will be compared in a similar manner as the primary endpoint. Tests of hypotheses will be two-sided and will be based on the contrasts between active sTMS and sham within the model.

For the Effectiveness of Blinding Questionnaire, descriptive statistics (sample size, mean, standard deviation) of the treater, rater, and patient blinding index will be presented at each visit (Treatment Day 5 and Treatment Day 30 [end of double-blind phase]) for each treatment group and both treatments combined as described by Bang et al (2004). A mean close to 0 indicates random blinding (or random guessing); a mean closer to 1 than 0 may indicate failure in blinding (majority of "guesses" were correct); a mean closer to -1 than 0 indicates mainly incorrect guesses were made.

11.6 SAFETY DATA

The assessment of safety will be based mainly on the frequency of adverse events recorded. Other safety data (e.g., vital signs and ECG) will not be collected systematically but will be considered as appropriate. All safety analyses will be performed on the Safety Population as defined above.

Adverse events will be summarized by presenting the number and percentage of subjects having any treatment emergent adverse event (TEAE; defined as an AE that started or worsened in severity following randomized treatment), and having any TEAE within each MedDRA system organ class and within each MedDRA preferred term. Patients with multiple occurrence of an event will be counted once within the given system organ class and preferred term. This analysis will be repeated for serious TEAEs. TEAEs will further be categorized for each individual AE by severity and relationship to study treatment.

The incidence of treatment-emergent adverse events by MedDRA system organ classes and preferred terms will be compared between active and sham treatment using Fisher's Exact test.

Other information collected will be listed as appropriate.

Statistical tests performed on safety data to explore the data will be used only to highlight any interesting comparisons that may warrant further consideration. Safety summaries will be performed for each of the active and sham treatment for all study subjects in the Safety Population.

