At the end of the 6-week double-blind treatment phase, all subjects who did not achieve remission were allowed to participate in a four-week open label treatment phase using the active NEST device and were assessed at the Week 10 time point (n = 89). Those subjects not eligible to participate in the open label phase were also assessed at the Week 10 time point (n= 31).

The primary efficacy endpoint for the study was mean HAM-D₁₇ total score change from Baseline (Day 0) to Week 6 compared between the active treatment and sham-controlled groups. Salient results for the Per Protocol patient cohort were as follows:

- The active sTMS treatment was shown to be significantly more effective than sham treatment for the primary efficacy endpoint (change in HAM-D₁₇ total score)
- The mean relative treatment effect (-9 Active vs. -6.56 Sham, $p=0.03$) is clinically significant and consistent with, or larger than, prior rTMS and antidepressant drug trials.
- Secondary Clinical Rating scales (HAM-D₂₄, HAM-D₂₈, IDS-SR, and MADRS) support efficacy in this population,
- There were no significant differences between Sham and Active sTMS treatment in incidence rates of:
 - Any AE
 - Intensity of AE's
 - Relationship to study treatment

- Clinically significant AE's
- Study drop-out rates
- The “open label” participants were observed to improve in their HAM-D₁₇ total score over the four-week treatment ($p = 0.01$).

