2 STUDY OBJECTIVE

The primary objective of this study is to confirm the safety and effectiveness of synchronized TMS (sTMS) therapy in subjects with Major Depressive Disorder who have not responded adequately to at least one antidepressant medication in the current episode.

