13.2 OTHER RISKS

The NeoSync sTMS device generates a weak magnetic field that is considered to be a small fraction of the exposure you would have from a single scan of your brain with an MRI machine. In previous studies with this device, the participants reported minimal side effects. In the prior NEST study, there was no significant difference in the rate of adverse reactions or early discontinuations in the active and sham treatment groups. Adverse events reported in both the “sham” and “active” treatment groups that were considered “possibly” related to the procedure were: Stiff Neck, Back Pain, Headache, Lightheadedness, Dizziness, Blurred Vision, and Insomnia. All of these events resolved and none resulted in discontinuation from the trial.

Other risks of this study are minor. Occasionally some emotional discomfort may occur while filling out questionnaires or being interviewed about matters pertaining to mood, functioning and other experiences. Subjects may experience minor discomfort during blood draws for laboratory tests. In addition, there may be minor skin irritation caused by the application of EEG electrodes.

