Adverse events will be summarized by presenting, for each treatment group, the number and percentage of subjects having any treatment emergent adverse event overall and by each MedDRA preferred term and by each MedDRA system organ class. A patient experiencing more than one adverse event within a given system organ class and preferred term will be counted once within that system organ class and preferred term. Adverse events will be presented separately for the 6-week phase, for the follow-up open-label phase, and for the entire study. A treatment emergent adverse event in the double-blind phase is defined as an event starting or worsening in severity at or after the start of double-blind treatment; a treatment emergent adverse event in the open-label phase is defined as an event starting or worsening in severity at or after the start of open-label treatment. Note that the adverse event frequencies in the open-label phase will be presented by the treatment the patient received in the double-blind phase, as well as for all subjects entering the open-label phase as one group.

The above will be repeated for treatment emergent serious adverse events

Adverse events will be summarized in a similar manner by severity and relationship to study device. Patients with more than one adverse event within a given system organ class and preferred term will be categorized into the maximum category (e.g., maximum severity) experienced for that system organ class and preferred term.

Other safety information collected during this study is:

1. Vital Signs and Weight: Baseline, Week 6 Evaluation Visit

Subjects' heart rate and blood pressure will be collected at Baseline and at the Week 6 Visit (or early termination visit if the subject discontinued prior to Week 6). Descriptive statistics of each variable will be presented at each visit for the safety population by double-blind treatment group. Descriptive statistics of the change from baseline will also be presented by treatment group.

2. Urine Toxicology Panels: Screening

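### The trial sets out to confirm safety, but no planned analysis estimates the sTMS-minus-sham difference in adverse events with an interval, so no output shows what excess harm has been ruled out.

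*Protocol*

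**What the plan says.** Protocol section 2 states: "The primary objective of this study is to confirm the safety and effectiveness of synchronized TMS (sTMS) therapy". The SAP's study objectives repeat this.

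For adverse events, Protocol 11.6 plans counts and percentages of subjects with TEAEs in the Safety Population. Incidence by MedDRA system organ class and preferred term "will be compared between active and sham treatment using Fisher's Exact test". The same section limits the role of these tests: they "will be used only to highlight any interesting comparisons that may warrant further consideration".

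SAP section J keeps the tabulations and drops the test: "Adverse events will be summarized by presenting, for each treatment group, the number and percentage of subjects having any treatment emergent adverse event overall", and then by preferred term and system organ class. Serious events, severity and relationship to the device are tabulated in the same way.

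Protocol 11.5 has general rules for tests ("All statistical tests will be two-sided with a significant level of 0.05 unless otherwise specified") and for intervals ("All confidence intervals will be two-sided with a confidence level of 95%, unless otherwise specified"), but no interval is assigned to adverse events. For the primary efficacy endpoint, Protocol 11.5 and the SAP both specify a 95% Newcombe-Wilson interval for the risk difference.

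**The concern.** An objective of confirming safety calls for some output showing how large an excess of harm the data exclude. Counts and percentages do not do that, and neither does a p-value. If the Fisher tests are only a screen, the plan contains no between-arm estimate with stated uncertainty on which a safety conclusion could rest. Neither document gives a safety hypothesis, margin or acceptance criterion. Change in C-SSRS is a named safety outcome in Protocol 10.3, but Protocol 11.6 and SAP section J specify no between-arm analysis of it.

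At stake is the wording of the safety conclusion. With about 60 subjects per arm, a table with no significant differences is compatible with moderate excesses of harm, and a reader of the planned tables could not see how large.

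**Working it through.** **Inputs from the documents.** Allocation is 1:1 with about 60 per arm (Protocol section 4). The Safety Population is everyone treated at least once (Protocol 11.1), so up to about 60 per arm, not the 46 per arm of the per-protocol set. The cap after re-estimation is 240 enrolled, or 120 per arm (Protocol 11.4). Tests are two-sided at 0.05 (Protocol 11.5).

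**Assumed.** All adverse event rates below; the documents give none.

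**Step 1: reproduce the plan's own power figure.** Protocol 11.4 states 81% power for 34% vs 8% at 46 per arm with Fisher's test. The continuity-corrected normal approximation gives 46 per arm at 81% power, and 81.4% when inverted at n = 46. Exact enumeration gives 83.6%. The stated figure is reproduced and slightly conservative.

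**Step 2: power of the safety test.** Power = Σᵢ Σⱼ Bin(i; n, p_active) · Bin(j; n, p_sham) · 1[Fisher p(i, j) ≤ 0.05], summed over all outcomes.

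| Sham vs sTMS (assumed) | Power, 60 per arm | Missed | Power, 120 per arm | Missed |
|---|---|---|---|---|
| 5% vs 15% | 32.6% | 67% | 67.4% | 33% |
| 10% vs 20% | 24.7% | 75% | 51.6% | 48% |
| 20% vs 35% | 37.5% | 62% | 70.0% | 30% |
| 0% vs 5% | 7.9% | 92% | 55.8% | 44% |
| 5% vs 25% | 84.5% | 15% | 99.3% | 1% |
| 10% vs 30% | 73% | 27% | 97% | 3% |
| 20% vs 40% | 60% | 40% | 91% | 9% |

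About 152 per arm would be needed for 80% power at 5% vs 15%.

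**Step 3: what an interval would show at 60 per arm.** With Wilson limits (l, u) for each arm and d = p₁ − p₂, the Newcombe limits are:

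- lower = d − √[(p₁ − l₁)² + (u₂ − p₂)²]
- upper = d + √[(u₁ − p₁)² + (p₂ − l₂)²]

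For 9/60 vs 3/60, the Wilson limits are 0.0810 to 0.2611 and 0.0171 to 0.1370, and d = 0.100.

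- Lower = 0.100 − √[(0.150 − 0.0810)² + (0.1370 − 0.050)²] = 0.100 − 0.111 = −0.011.
- Upper = 0.100 + √[(0.2611 − 0.150)² + (0.050 − 0.0171)²] = 0.100 + 0.116 = 0.216.

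| Events, sTMS vs sham | Fisher p | Difference, points | 95% interval, points |
|---|---|---|---|
| 9 vs 3 | 0.125 | +10.0 | −1.1 to +21.6 |
| 5 vs 0 | 0.057 | +8.3 | +0.7 to +18.1 |
| 3 vs 3 | 1.00 | 0 | −9.3 to +9.3 |
| 1 vs 1 | 1.00 | 0 | −7.3 to +7.3 |

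All four rows would be reported as not significant. Their upper limits run from about 7 to about 22 points, and neither document's planned output shows this.

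**The case against.** The strongest reply is that the plan does not treat non-significance as safety. Protocol 11.6 confines the tests to screening, bases safety mainly on adverse event frequencies, and adds seriousness, severity and relatedness. The SAP adds vital signs and reasons for discontinuation by arm. This is a descriptive assessment that was never powered as a test. If the SAP governs, there is no safety p-value to misread.

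Most of this stands. A reader might infer that a non-significant result would be reported as confirmed safety, because the protocol describes the previous trial that way: "There were no significant differences between Sham and Active sTMS treatment in incidence rates of" several adverse event measures (section 1.1), and in section 13.2 "there was no significant difference in the rate of adverse reactions or early discontinuations in the active and sham treatment groups". Those are background and risk statements about an earlier study. They set no decision rule for this one, and the documents do not support the stronger reading.

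It would also be wrong to say that the test usually misses any doubling or tripling of an event rate. At 60 per arm, 10% vs 30% is detected about 73% of the time and 20% vs 40% about 60%. The low power applies to moderate excesses.

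Finally, an interval alone does not define an acceptable excess. That is true: the fix shows what has been excluded but sets no margin. What the reply does not answer is that a descriptive assessment, with no interval, is all that supports an objective worded as confirmation.

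**Conclusion.** The point holds as a gap in the planned safety output. The objective is to confirm safety, and neither document plans an adverse event risk difference or interval. The only between-arm safety test is an exploratory one that appears in the protocol and not in the SAP.

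At the planned size that test has about 33% power for an assumed 5% vs 15%. At the cap, which is reached only if the interim rule increases the sample, it has about 67%. These figures rest on assumed event rates and on nearly all randomized subjects being treated. Non-significance could not support a claim of confirmed safety against moderate excesses, although Protocol 11.6 makes no such claim. The efficacy inference is unaffected. This is a low-cost improvement that bears directly on a stated primary objective.

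**What to change.** In Protocol 11.6 and SAP section J, for the double-blind phase in the Safety Population, present the sTMS-minus-sham risk difference with a two-sided 95% Newcombe-Wilson interval for:

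- any TEAE
- any serious TEAE
- any device-related TEAE
- discontinuation due to an adverse event
- each preferred term occurring in at least 5% of either arm.

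Add a statement such as: *The safety conclusion will rest on the estimated risk differences and their upper 95% confidence limits; a non-significant difference will not be interpreted as no difference.*

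Align the two documents on whether Fisher p-values are reported. If they are kept, label them as a screening flag only and say that the interval takes precedence, since the two can disagree (5 vs 0 above).

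The cost is a few sentences and extra columns in tables already planned, using a method already specified for efficacy. The downside is a less favourable safety statement, because upper limits become visible: about 7 to 9 points for balanced rare events and about 20 points for splits such as 9 vs 3.
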